
Datasets required to identify vaccinated individuals
	
 • Data from the National Clinical Data Store (NCDS). Information recorded on the National Vaccine Management Tool (VMT) and GPIT system (Primary care practice medical record database) flows to the

² Stock SJ, McAllister D, Vasileiou E, *et al.* COVID-19 in Pregnancy in Scotland (COPS): protocol for an observational study using linked Scottish national data. *BMJ Open* 2020;**10**:e042813. doi: 10.1136/bmjopen-2020-042813. Available from: [COVID-19 in Pregnancy in Scotland \(COPS\): protocol for an observational study using linked Scottish national data | BMJ Open](#)

	NCDS, from where it is cleaned and then linked to the COPS data. Relevant data of interest: vaccination date, type, dose.
Datasets required to identify outcomes of interest	
 Data from a number of sources that hold pregnancy, maternal and neonatal outcome data will be brought into the COPS study dataset. Sources include: SMR01, SMR02, national linked anomaly database, SICSAG critical care admissions, NRS deaths.

3.5: Study Variables

3.5.1: Study Outcomes

Maternal, pregnancy and neonatal outcomes of interest are listed in Table 2. In our main analyses, we will assess the risk of each outcome in vaccinated women and their unvaccinated controls (i.e. classifying each woman as having the outcome or not), and will not attempt to capture any differences between the groups in the time to these events. As noted in Table 2, there are different periods of risk for each outcome (referred to as “outcome-specific follow-up period” throughout this protocol). For example, women will be considered at risk of any miscarriage from conception up to 23⁺⁶ weeks gestation, and at risk for stillbirth from 24⁺⁰ weeks gestation to the end of pregnancy. Women without an observed outcome who had not completed follow-up to the end of the follow-up period for a specific outcome in either the pre-pandemic (i.e. outcome-specific follow-up period not completed before 01 March 2020) or in the pandemic time period (i.e. outcome-specific follow-up period not completed before date of data extraction) will not be eligible for inclusion in the analysis for that outcome.

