Outcomes have been aligned as far as possible with the relevant Brighton/GAIA outcome definitions, and also agreed with those in the MHRA / four nations working group on COVID-19 vaccination in pregnancy and comply with those recommended by the WHO³. See Appendix 2 for full rational and sources of information behind included outcomes, definitions, timings etc. as presented in Table 2.

Both primary and secondary outcomes are of interest, with the former being a composite measure including the associated secondary outcomes, and the latter being a narrower measure or subset of the associated primary outcome, e.g. primary outcome = small for gestational age, secondary outcome = very small for gestational age.

Venous thromboembolism in pregnancy is a standard maternal outcome that may be influenced by infection or vaccination and is not the same as vaccine associated thrombosis with thrombocytopenia (VATT), the condition associated with the AstraZeneca vaccine⁴. Similarly, the pregnancy related bleeding outcome includes disseminated intravascular coagulation (DIC) which can occur in association with massive obstetric haemorrhage: again, this is distinct from VATT. Full lists of ICD10 codes used to identify the maternal outcomes venous thromboembolism, pregnancy-related bleeding, and hypertensive disorders of pregnancy are shown in Appendix 1.

³ <https://www.who.int/publications/m/item/safety-surveillance-of-covid-19-vaccines-in-pregnant-and-breastfeeding-women>

⁴ Pavord, S et al (2021). Clinical Features of Vaccine-Induced Immune Thrombocytopenia and Thrombosis. NEJM. DOI: 10.1056/NEJMoa2109908

'Clean windows' will be applied to outcomes, where appropriate, so that only new or incident cases occurring post vaccination will be counted. Specifically, a clean window of the current pregnancy will be applied for the venous thromboembolism, pregnancy-related bleeding, and hypertensive disorders of pregnancy outcomes (i.e. women will only be included if there is no prior record of these outcomes in the current pregnancy). See Table 2. For both congenital anomalies and pregnancy-related bleeding, further descriptive analyses will be conducted looking at more specific diagnoses within these broader outcome groups if we find evidence for an association between vaccination and these outcomes. For example, for pregnancy-related bleeding, we can further disaggregate into early pregnancy bleeding, obstetric haemorrhage, and DIC.

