For the matched cohort study, the primary comparison for each outcome will be between women vaccinated in the six weeks preceding conception or up to the end of the outcome-specific exposure period within pregnancy and unvaccinated pregnant women from the pre-pandemic period. Only women who had been followed-up to the end of the outcome-specific follow-up period on the 29 February 2020 are eligible to be controls for that outcome analysis. Women who have COVID-19 infection from six weeks preconception up to the end of the outcome-specific follow-up period will

not be eligible for inclusion in the vaccinated group for this primary analysis. Each individual in the pregnant vaccinated cohort will be matched to three individual unvaccinated pregnant controls, if possible⁵. Different pregnancies from a single woman can be matched to different cases, and if a case had a pregnancy in the pre-pandemic period, that pregnancy is a valid control, as long as the woman is not matched to herself. Here the assumption is that pregnancies are independent. A sensitivity analysis will be conducted, removing women who are vaccinated in the six weeks preconception – and her controls – from the analysis.

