With the pre-pandemic period being used as the baseline, there is an assumption that the pandemic has not substantially affected the outcomes of interest through, for example, changes in engagement and provision of maternity services. To investigate this, a supplementary analysis will be conducted with pregnant unvaccinated controls from the pandemic vaccination period (from 08 December 2020 to date of data extraction). In this supplementary analysis, we will exclude women (from both the vaccinated and unvaccinated group) who had any record of COVID-19 infection from six weeks preconception to the end of the outcome-specific follow-up period. However, given that there is potential for vaccination to impact on maternal, pregnancy and neonatal outcomes by changing the risks of acquiring COVID-19 and experiencing severe illness, we will also conduct a second supplementary analysis with pregnant unvaccinated controls from the pandemic. In this, we will retain both vaccinated and unvaccinated women with a confirmed record of COVID-19 infection during pregnancy and preceding the end of the outcome-specific follow-up period. For both these supplementary analyses, women who were vaccinated >6 weeks pre-conception will be included in the control group (as not vaccinated in pregnancy), however sensitivity analyses (if sample size permits) will be conducted to investigate any differences between pairs where the control is completely unvaccinated versus pairs where the control received vaccination >6 weeks pre-conception (e.g. vaccinated pre-‘pregnancy’). Additional supplementary analyses removing women who are vaccinated in the six weeks preconception will be considered for the analyses using women from the pandemic period as controls, if we observe an impact of removing these women in the primary analysis using pre-pandemic controls.

Maternal and gestational age are known to be important risk factors for adverse events in pregnancy (e.g. miscarriage strongly influenced by maternal age). Consequently, the cohorts will be matched by maternal age (± 1 years but relaxed (i.e. possibly $\pm >1$ year) at the tails of maternal age distribution as fewer individuals available for matching), and gestational age (exact match, i.e. same week however allow for relaxation of this at the tails of the gestation distribution).

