In addition, vaccinated pregnant women will also be matched by season of conception (quarter) to historical controls from the pandemic and pre-pandemic periods due to the seasonality of some outcomes. It is not necessary to do this for contemporary controls (from the pandemic vaccination period) as those pairs will be matched by calendar date (i.e. matching a vaccinated woman by maternal and gestational age, on the day of vaccination to a control of the same maternal and gestation age, on the same date).

For comparisons between vaccinated and unvaccinated matched individuals, the index date (reference point for matching maternal and gestational age, and season of gestation for analyses involving controls from historical periods only) will be the date of vaccination.

⁵ Donegan K, King B, Bryan P. Safety of pertussis vaccination in pregnant women in UK: observational study BMJ 2014; 349:g4219 doi:10.1136/bmj.g4219. Available from: <https://www.bmj.com/content/349/bmj.g4219>

The matching strategy for each of the three analyses is shown in Table 5.

Table 5: Matching strategy for each analysis of the matched cohort study

Analysis	Time period for control group*	Matched three controls to each case by:	Notes
Primary analysis	Pre-pandemic period (01 January 2015 to 29 February 2020)	
 Maternal age Gestational age Season of conception (quarter) 	
 Aim to match to three unvaccinated controls Maternal age matched by ± 1 year but relaxed at tails of maternal age distribution Gestational age matched by same week but relaxed at tails of the gestation distribution
Supplementary analysis 1	Pandemic vaccination period (from 08 December 2020 to date of data extraction), excluding cases and controls with confirmed COVID-19 between six weeks preconception to end of outcome-specific follow-up period	
 Maternal age Gestational age 	
Supplementary analysis 2	Pandemic vaccination period (from 08 December 2020 to date of data extraction), including cases and controls with confirmed COVID-19 between six weeks preconception to end of outcome-specific follow-up period	
 Maternal age Gestational age 	

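### Pre-pandemic controls are matched on gestational week without a day on which they must still be pregnant, which can bias the primary analysis modestly towards apparent protection

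*Protocol*

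**What the plan says.** Section 3.6 of the protocol sets the gestational match as "gestational age (exact match, i.e. same week however allow for relaxation of this at the tails of the gestation distribution". Table 5 gives the same rule for the primary analysis: "Gestational age matched by same week but relaxed at tails of the gestation distribution". The index date "will be the date of vaccination".

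For contemporary controls, section 3.6 turns that date into a condition on the control: a vaccinated woman is matched "on the day of vaccination to a control of the same maternal and gestation age, on the same date". For pre-pandemic controls no equivalent is given. They are matched on maternal age, gestational week and quarter of conception. Beyond that, the stated conditions are that a woman is not matched to herself and that follow-up is complete: "Only women who had been followed-up to the end of the outcome-specific follow-up period on the 29 February 2020 are eligible to be controls".

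Two other parts of the plan bear on the point. Section 3.5.1 treats each outcome as yes or no and "will not attempt to capture any differences between the groups in the time to these events". It also says that "a clean window of the current pregnancy will be applied for the venous thromboembolism, pregnancy-related bleeding, and hypertensive disorders of pregnancy outcomes"; Table 2 lists no clean window for miscarriage, stillbirth, preterm birth or extended perinatal mortality. Appendix 3, Match 1, uses the same kind of historical control for the infection analysis.

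**The concern.** A woman vaccinated at 12+6 was necessarily pregnant at 12+6. A pre-pandemic pregnancy that miscarried at 12+1 reached the same gestational week, so nothing in the matching rule excludes it as her control, although it ended five days before the vaccinated woman's index gestation. Its miscarriage would count as a control event. Controls are then at risk from day 0 of the week and vaccinated women only from the vaccination day. This is a short stretch of immortal time on the vaccinated side.

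Nothing later in the analysis removes such a control. The outcome is binary, these outcomes have no clean window, and gestational week in the multinomial model cannot correct a difference within the week. It also sits badly with the aim in section 3.5.1 of counting only incident events after vaccination.

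The affected outcomes are primary ones in the primary analysis of a safety study, where a bias towards protection can mask harm. The contemporary-control analyses are largely free of the problem. A gap between them and the primary analysis could therefore be misread as an effect of the pandemic on outcomes, which is what the first supplementary analysis is meant to detect.

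**Working it through.** The protocol states no figure for this bias, so there is none to reproduce. The check asks what RR the week-only rule gives when vaccination has no effect.

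**Inputs from the protocol.** Table 2: miscarriage risk 10-20%, window closing at 23+6; preterm birth 7%, window closing at 36+6; very preterm birth (before 32 weeks) 1%. Section 3.5.2: exposure starts six weeks before conception.

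**Assumptions, since the protocol gives no weekly hazards or vaccination timing.**
- Miscarriage hazard starts at week 5. It is either flat or falls by a factor e every 3 weeks, scaled to a total of 10% or 20%.
- Preterm hazard rises exponentially from week 24, fitted to 1% before 32 weeks and 7% before 37 weeks (rate 0.387 per week).
- Vaccination is spread evenly over weeks and over days within a week.

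**Formulas.** Let S(d) be the probability that the pregnancy is still ongoing at gestational day d, and T the end of the outcome window (day 168 for miscarriage, 259 for preterm birth).
- Control risk for week w: R_C(w) = 1 − S(T)/S(7w).
- Vaccinated risk for week w: R_V(w) = average over k = 0 to 6 of 1 − S(T)/S(7w + k).
- Pooled RR = mean of R_V over weeks ÷ mean of R_C over weeks.

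**Pooled results with no vaccine effect.**

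| Outcome and vaccination weeks | R_V | R_C | RR |
|---|---|---|---|
| Miscarriage 10%, flat, weeks 2-23 | 0.0579 | 0.0598 | 0.97 |
| Miscarriage 10%, falling, weeks 2-23 | 0.0278 | 0.0299 | 0.93 |
| Miscarriage 20%, flat, weeks 2-23 | 0.1175 | 0.1214 | 0.97 |
| Miscarriage 20%, falling, weeks 2-23 | 0.0564 | 0.0605 | 0.93 |
| Preterm birth, weeks 2-36 | 0.0652 | 0.0660 | 0.99 |
| Preterm birth, weeks 24-36 | 0.0572 | 0.0593 | 0.96 |

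Odds ratios, which the protocol will report, differ from these by no more than 0.004.

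**Adding the six preconception weeks.** These carry no bias: both groups have the full risk. For miscarriage at 10%:
- Flat: (22 × 0.0579 + 6 × 0.10) ÷ (22 × 0.0598 + 6 × 0.10) = 1.874 ÷ 1.916 = 0.98.
- Falling: (22 × 0.0278 + 0.60) ÷ (22 × 0.0299 + 0.60) = 1.212 ÷ 1.258 = 0.96.

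The 20% cases give the same two values. For preterm birth, adding these weeks moves 0.99 still closer to 1.

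**Sensitivity to timing.** Under the falling hazard, vaccination confined to weeks 5-13 or 5-23 gives 0.87-0.88 for miscarriage. Preterm birth gives 0.93 for weeks 30-36. In the last week of a window the ratio is far lower: 0.54-0.57 for miscarriage in week 23, and 0.0141 ÷ 0.0232 = 0.61 for preterm birth in week 36. With a flat hazard the last-week value follows directly: vaccinated women are at risk for (7 + 6 + 5 + 4 + 3 + 2 + 1)/7 = 4 days on average and controls for 7, and 4/7 = 0.57.

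**Other readings of the rule.** If a control must be pregnant on the same gestational day, R_C(w) equals R_V(w) and the RR is 1.00 by construction. If she must complete the whole week, the bias reverses. Over weeks 2-23 miscarriage gives 0.0579 ÷ 0.0553 = 1.05 (flat) and 0.0278 ÷ 0.0253 = 1.10 (falling). Across all the timings tried, the range is 1.04-1.21 for miscarriage and 1.02-1.14 for preterm birth.

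**The case against.** The strongest reply is that the protocol nowhere says that an ended pregnancy may serve as a control. A reader might infer that it does, but that follows only from the absence of an exclusion. Some wording points the other way. The comparators are called pregnant, an index date at which gestational age is matched suggests a pregnancy in progress, and section 4.3 plans plots of time from vaccination or matching to outcome, which would be negative for a control whose pregnancy had already ended. This stands as a limit on the claim. It does not settle the rule, because no sentence names the day on which the control must be pregnant, and the only gestational criterion given is the week.

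It can also be said that contemporary controls have no explicit still-pregnant rule either. True, but having a given gestational age on a given calendar date implies it. A same-week match to a pregnancy from years earlier does not.

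A third reply is that this is detail for an analysis plan. Finer implementation could be left there, but the protocol itself fixes the unit of matching, and that unit is what produces the bias.

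On size, a reader might take the ratios of 0.54-0.61 as the effect on the primary estimate. The protocol does not support that: they apply only to vaccination in the last week of a window, and no week-specific estimate is planned. Nor can the effect of relaxing the match at the tails be sized, since neither its extent nor its direction is given.

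The supplementary analyses are a partial safeguard, but they differ from the primary analysis in other ways and are not a clean test.

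**Conclusion.** The point holds as a modest, avoidable bias in the primary analysis if the matching rule is applied as written. It is confined to outcomes that end pregnancy: miscarriage, preterm birth, and by the same mechanism stillbirth and extended perinatal mortality, for which no size was computed. It is negligible for ectopic pregnancy, where exposure closes at 2+6, and little is expected for measures taken at birth such as birthweight or Apgar score.

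With no true effect, the pooled RR is about 0.96-0.98 for miscarriage over the full exposure window and about 0.99 for preterm birth over weeks 2-36. Larger distortions need vaccination concentrated in the weeks that carry the hazard, above all near the end of a window. All sizes rest on the assumed hazards and even timing. The documents do not support the stronger statement that the plan admits ended pregnancies by design or makes vaccination look strongly protective. Because the direction depends on which reading of same week is programmed, the rule needs stating whichever was meant.

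**What to change.** In section 3.6, Table 5 and Appendix 3 Match 1, state the following for pre-pandemic controls:
- Each control receives an index day: the day on which her pregnancy reached the exposed woman's gestation, in weeks and days, at vaccination (or at infection in Appendix 3).
- Her pregnancy must be ongoing and free of the outcome on that day, including where the week match is relaxed at the tails.
- Outcomes are counted from that day in both groups.

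The change costs a sentence or two and one filter in the matching code. Table 2 already works in weeks and days. The loss of candidate controls from a pool of about five years should be negligible. The remaining weakness is that conception dates are imputed (section 5.0), so gestation in days carries error and some residual day-level bias can persist.

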Any congenital anomaly (relevant pregnancy outcome only)	Any major congenital anomaly as defined by EUROCAT (including live born babies diagnosed at <28 days of age and affected pregnancies resulting in spontaneous loss at ≥20 weeks or termination of pregnancy at any gestation)	Primary	None	Up to 9+6 gestation	At E plus NN	2.7
• Any non-genetic congenital anomaly (relevant pregnancy outcome only)	Any major congenital anomaly as defined by EUROCAT, excluding anomalies with known underlying genetic basis as per standard EUROCAT rules (including live born babies diagnosed at <28 days of age and affected pregnancies resulting in spontaneous loss at ≥20 weeks or termination of pregnancy at any gestation)	Secondary	None	Up to 9+6 gestation	At E plus NN	2.3
Microcephaly	Congenital microcephaly (i.e. present at birth) OFC on delivery record <2SD below	Primary	None	Any	At E	2.0

	mean for sex and gestation at delivery by WHO-UK90 growth reference Babies with anencephaly excluded					
• Severe microcephaly	Congenital microcephaly (i.e. present at birth) OFC on delivery record <3SD below mean for sex and gestation at delivery by WHO-UK90 growth reference Babies with anencephaly excluded	Secondary	None	Any	At E	0.4
Preterm birth	Delivery at <37 completed weeks gestation	Primary	None	Up to 36+6 gestation	Up to 36+6 gestation	7.0
• Very preterm birth	Delivery at <32 completed weeks gestation	Secondary	None	Up to 31+6 gestation	Up to 31+6 gestation	1.0
Spontaneous preterm birth	Delivery at <37 completed weeks gestation following P-PROM or spontaneous onset of labour	Primary	None	Up to 36+6 gestation	Up to 36+6 gestation	4.0
• Spontaneous very preterm birth	Delivery at <32 completed weeks gestation following P-PROM or spontaneous onset of labour	Secondary	None	Up to 31+6 gestation	Up to 31+6 gestation	0.6
Small for gestational age	Birthweight <10th centile by WHO-UK90 growth reference	Primary	None	Any	At E	10.0
• Very small for gestational age	Birthweight <3rd centile by WHO-UK90 growth reference	Secondary	None	Any	At E	3.0
Low Apgar score	5 min Apgar <7	Primary	None	Any	At E	1.5
• Very low APGAR score	5 min Apgar <4	Secondary	None	Any	At E	0.5
Neonatal death	Death from any cause	Primary	None	Any	E plus NN	0.2
Extended perinatal mortality (total births)	Stillbirth or neonatal death from any cause	Primary	None	Any	Up to E plus NN	0.6

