Notes: If timing of vaccination during pregnancy is specified as 'any', this means that women vaccinated at any point from six weeks preconception to date of end of pregnancy (E) will potentially be included in the analysis dependent on the woman being followed-up to the end of the outcome-specific follow-up period. For longer term risk periods: E is date of end of pregnancy; PP is mother's postpartum period, i.e. 6 weeks following delivery (E to E+41); NN is baby's neonatal period, i.e. 4 weeks following live birth (E to E+27). The pregnancy specific maternal outcomes listed above require follow-up to the end of the postpartum period (E+41) for mothers and the end of the postnatal period (E+27) for babies.

3.5.2: Exposure

The primary exposure to be investigated in the analyses is **any** receipt of COVID-19 vaccine from six weeks before conception to the end of an outcome-specific exposure period within pregnancy (Yes/No). The exposure periods for vaccination varies for each outcome (referred to as “outcome-specific exposure period” throughout this protocol), as outlined in Table 2. For ectopic pregnancy, for example, the exposed group will include women who were vaccinated between six weeks before conception up to 2⁺⁶ weeks gestation, while for stillbirth the vaccine exposure period is extended up to the end of the pregnancy.

Subgroup analyses will be conducted where sample size permits, further stratifying women who received their COVID-19 vaccine within the outcome-specific exposure period by: (1) the number of doses received; (2) by the class of vaccine(s) received and; (3) by the type of vaccine(s) received. For the latter two subgroup analyses, we will exclude women who received multiple different classes or types of vaccine within the outcome-specific exposure period. These results will need to be interpreted with caution given that some types of vaccination will be linked to specific sub-groups of women. For example, early in the vaccination programme women who were frontline health or care workers were more likely to receive the Pfizer/BioNTech vaccine, whereas women who were clinically (extremely) vulnerable were more likely to receive the AstraZeneca vaccine. There is therefore potential for residual confounding in comparative analyses examining outcomes following receipt of specific vaccine types.

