*Note that only women who have been followed-up to the end of the outcome-specific follow-up period at the end of each study period (i.e. 29 February 2020 for pre-pandemic controls and data of data extraction for pandemic controls) are eligible to be controls for a given outcome analysis.

3.7: Power calculation for matched cohort

It is estimated that by the end of 2021, full outcome and follow-up data will be available for approximately 5,000 vaccinated pregnant women, and by end of 2022, data available for 10,000 vaccinated pregnant women⁶.

Outcomes can be grouped as frequent (risk approximately 10%), moderate (approximately 3%), and rare (approximately 0.5%). Risk estimates for each adverse outcome are provided in Table 2. Based on these estimates and assumptions, with the relative risk of an event occurring post-vaccination set at 0.5, 1.2 and 2.0, and with statistical significance set at 0.05 and 0.01; power calculations for the various scenarios were calculated and are shown in Table 6. The power to detect a relative risk of 0.5, based on 5000 vaccinated pregnant woman against 15000 controls (ratio 1:3), when estimated

⁶ Personal communication with [name], July 2021.

adverse event occurrence is 0.5%, is 94%. This means that the study has a 94% chance of having a p-value of less than 5% (a statistically significant result and strong evidence against the null hypothesis) if there is really a difference in risk between vaccinated and unvaccinated women.

If the statistical power is low, the study sample size may be too small to detect any differences (i.e. under-powered) and therefore null results will need to be interpreted with caution. By convention, 80% is an acceptable level of power. It is acknowledged that the study may be under-powered to identify rarer outcomes.

Table 6: Power calculations scenarios

Cases	Controls	Estimated risk	Relative risk	Power %
5000	15000	0.50%	0.5	94
			1.2	10
			2.0	66
		3.00%	0.5	100
			1.2	45
			2.0	100
		10.00%	0.5	100
			1.2	94
			2.0	100
10000	30000	0.50%	0.5	100
			1.2	17
			2.0	94
		3.00%	0.5	100
			1.2	75
			2.0	100
		10.00%	0.5	100
			1.2	100
			2.0	100

4.0: Data Analyses

4.3: Descriptive analyses

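### Table 6 uses one count of vaccinated women for all outcomes, so the power it implies for ectopic pregnancy and, at a small effect, congenital anomaly is overstated

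*Protocol*

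**What the plan says.** Section 3.7 gives two totals. The first is that "full outcome and follow-up data will be available for approximately 5,000 vaccinated pregnant women" by the end of 2021; the second is "by end of 2022, data available for 10,000 vaccinated pregnant women". Both come from a personal communication and neither is broken down by outcome. Outcomes are grouped into risk classes of about 10%, 3% and 0.5%, with the reader sent to Table 2 for each outcome's risk. Table 6 then gives power for 5,000 against 15,000 and 10,000 against 30,000, with the "relative risk of an event occurring post-vaccination set at 0.5, 1.2 and 2.0".

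The exposed group is defined elsewhere, separately for each outcome. For ectopic pregnancy, section 3.5.2 says "the exposed group will include women who were vaccinated between six weeks before conception up to" 2+6 weeks. For congenital anomaly, Table 2 gives the vaccination timing as "Up to 9+6 gestation". For first-trimester miscarriage the limit is 13+6 weeks. Section 3.6 adds that vaccinated women with COVID-19 infection from six weeks preconception to the end of follow-up will "not be eligible for inclusion in the vaccinated group for this primary analysis". Section 3.7 mentions neither the windows nor this exclusion.

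**The concern.** A woman vaccinated at 25 weeks can be one of the 5,000, but she is not exposed for the ectopic or the anomaly analysis. For these outcomes the number in Table 6 is therefore not the number the analysis will have.

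Power matters here because of how the protocol uses it: section 3.7 treats 80% as acceptable and asks for caution with null results where power is low. A reader who finds ectopic pregnancy (1.0%) between the 0.5% and 3% rows would conclude that a doubling of risk is likely to be detected. If the eligible group is a fraction of 5,000, a null result would be taken as more reassuring than it is, for an outcome tied to vaccination around conception.

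**Working it through.** **Inputs from the protocol.** Totals 5,000 and 10,000, ratio 1:3, RR 0.5, 1.2 and 2.0 (section 3.7); background risk 1.0% for ectopic pregnancy and 2.7% for any congenital anomaly (Table 2); exposure windows from six weeks preconception to 2+6 and 9+6 weeks (Table 2, section 3.5.2). Alpha is two-sided 0.05. The text also names 0.01, but Table 6 has one power column and it matches 0.05.

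**Formula.** Two proportions, pooled variance under the null. With n1 vaccinated, n0 = 3·n1 controls, p0 the control risk, p1 the vaccinated risk and p̄ = (n1·p1 + n0·p0)/(n1 + n0):

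- s0 = √[p̄(1 − p̄)(1/n1 + 1/n0)]
- s1 = √[p1(1 − p1)/n1 + p0(1 − p0)/n0]
- power = Φ[(|p1 − p0| − 1.96·s0)/s1]

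**Step 1: reproduce Table 6.** With p1 = p0 × RR, as the text is worded, 5,000 women and risk 0.5% give 66%, 14% and 95% for RR 0.5, 1.2 and 2.0. Table 6 prints 94, 10 and 66. With the RR inverted (p1 = p0/RR), all 18 cells agree to within a point:

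| n vaccinated | Risk | RR 0.5: calculated (printed) | RR 1.2 | RR 2.0 |
|---|---|---|---|---|
| 5,000 | 0.5% | 94.8 (94) | 10.1 (10) | 66.5 (66) |
| 5,000 | 3% | 100 (100) | 44.7 (45) | 100 (100) |
| 5,000 | 10% | 100 (100) | 94.2 (94) | 100 (100) |
| 10,000 | 0.5% | 99.9 (100) | 16.9 (17) | 94.1 (94) |
| 10,000 | 3% | 100 (100) | 74.5 (75) | 100 (100) |
| 10,000 | 10% | 100 (100) | 99.9 (100) | 100 (100) |

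The cells use the full 5,000 or 10,000, so nothing was taken off for windows or infection. From here the RR is applied as worded.

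**Step 2: eligible numbers.** The protocol does not give the share vaccinated in each window. Assumption: vaccination is spread evenly from six weeks before conception (conception at 2+0) to 40+0, which is 6 + 38 = 44 weeks.

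- Ectopic pregnancy: 6 + 1 = 7 weeks; 7/44 = 15.9%; about 795 of 5,000 and 1,591 of 10,000.
- Congenital anomaly: 6 + 8 = 14 weeks; 14/44 = 31.8%; about 1,591 of 5,000 and 3,182 of 10,000.

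**Step 3: two examples at 5,000.**

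- Ectopic, RR 2.0: p0 = 0.010, p1 = 0.020, p̄ = 0.0125, s0 = 0.00455, s1 = 0.00537. Power = Φ[(0.0100 − 0.00892)/0.00537] = Φ(0.20) = 58%.
- Anomaly, RR 1.2: p0 = 0.0270, p1 = 0.0324, p̄ = 0.02835, s0 = 0.00480, s1 = 0.00502. Power = Φ[(0.0054 − 0.00942)/0.00502] = Φ(−0.80) = 21%.

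**Step 4: results.** The last column halves the share and multiplies it by 1.5.

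| Outcome | Total | RR | Power, full total | Power, even spread | Range at 0.5-1.5 × share |
|---|---|---|---|---|---|
| Ectopic (1.0%) | 5,000 | 2.0 | 99.9% | 58% | 37-73% |
| Ectopic | 5,000 | 0.5 | 94% | 22% | 11-34% |
| Ectopic | 10,000 | 2.0 | 100% | 84% | 58-94% |
| Anomaly (2.7%) | 5,000 | 1.2 | 51% | 21% | 13-29% |
| Anomaly | 10,000 | 1.2 | 79% | 36% | 21-50% |
| Anomaly | 5,000 | 0.5 | 100% | about 90% | 60-98% |
| Anomaly | 5,000 | 2.0 | 100% | 99.7% | 93-100% |

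For ectopic pregnancy, 80% power at RR 2.0 needs about 1,435 exposed women. That is 29% of 5,000, inside a window of about seven weeks.

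**Step 5: infection exclusion alone.** The protocol gives no count. At 0.5% risk with the RR as worded, removing 5% (5,000 to 4,750) lowers power at RR 0.5 from 66.5% to 63.9%; removing 20% lowers it to 55%.

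**The case against.** Table 6 is laid out by risk class, not by outcome. Ectopic pregnancy has no row of its own, and only congenital anomaly lies close to a printed risk (2.7% against 3%). This stands to the extent that the power is implied rather than printed. But section 3.7 sends the reader from the risk classes to Table 2, so the table is meant to be read outcome by outcome.

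The even spread is only a model. Any dose inside the window counts as exposure, so a woman first vaccinated earlier can enter through a later dose. If a second dose follows 8-12 weeks later (an assumption), the ectopic share rises to about 25-27% and power at RR 2.0 to about 75-78%. Section 4.4 also allows ongoing pregnancies in the reference group for early outcomes, which might add women. The calendar points the other way for anomaly. A woman vaccinated by 9+6 who delivers at 40+0 and completes E+27 by 31 December 2021 was vaccinated by about 7 May 2021, three weeks after the guidance of 16 April. The direction of the error is clear; its size is not fixed.

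The protocol does warn of low power, in sections 3.7 and 5.0. That warning concerns rare outcomes and does not mention narrow exposure windows. For anomaly at RR 1.2 it carries some weight, since Table 6 already shows only 45% in the 3% row at 5,000.

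A reader might infer three stronger claims that the protocol does not support:

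- **Anomaly power collapses generally.** Under even spread it stays at about 90% or more at RR 0.5 and 2.0. An RR such as 1.5 would show a larger loss, but it is not a Table 6 scenario.
- **First-trimester miscarriage has a known loss.** Table 2 gives its background risk as unknown, and its follow-up ends at 13+6, so women outside the fully followed 5,000 may qualify. Scaling 5,000 by 18/44 is not sound.
- **The infection exclusion is a main cause.** It costs little unless it removes a large share.

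**Conclusion.** The point holds for ectopic pregnancy and, at RR 1.2, for congenital anomaly. That a single total is used for every outcome, against the protocol's own exposure rules, can be seen from the text and from the reproduction of Table 6, and needs no assumption. The size depends on the assumed timing of vaccination.

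The serious case is ectopic pregnancy at 5,000, where power at RR 2.0 stays below 80% across the tested range. At 10,000 and even spread it reaches about 84%. For anomaly the loss at RR 1.2 deepens a weakness that Table 6 already shows at 5,000; at 10,000 it turns a nearly adequate 79% into 36%. First-trimester miscarriage is affected in the same direction, but no figure can be fixed from the protocol.

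This is a fault in stated power, not in design or analysis. It should be corrected because section 3.7 makes the reading of null results depend on power.

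**What to change.** In section 3.7, give the expected number of eligible vaccinated women for each exposure window, net of the infection exclusion. Use observed counts to date from the linked COPS and vaccination data, and project them with a stated range for the forecast totals, since section 5.0 notes that recent early-pregnancy vaccinations are picked up late. Restate power for ectopic pregnancy and congenital anomaly on those numbers, with each outcome's own Table 2 risk. For first-trimester miscarriage, either state an assumed background risk and count eligible women by its own follow-up rule, or say that power is not given.

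When recalculating, apply the RR in the direction the text describes, because the present table reproduces only with it inverted. The 94% worked example at RR 0.5 and 0.5% risk then becomes 66%. The text also announces power "with statistical significance set at 0.05 and 0.01": show which alpha each figure uses, or drop the second.

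The cost is one recalculated table and less favourable stated power for these outcomes. Design, matching and analysis stay as they are.
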